4	xx (xx.x)	xx (xx.x)	xx (xx.x)	xx (xx.x)
5	xx (xx.x)	xx (xx.x)	xx (xx.x)	xx (xx.x)
6	xx (xx.x)	xx (xx.x)	xx (xx.x)	xx (xx.x)
7	xx (xx.x)	xx (xx.x)	xx (xx.x)	xx (xx.x)
8	xx (xx.x)	xx (xx.x)	xx (xx.x)	xx (xx.x)
...				
28	xx (xx.x)	xx (xx.x)	xx (xx.x)	xx (xx.x)
n	xxx	xxx	xxx	xxx
Mean	xx.x	xx.x	xx.x	xx.x
SD	xx.x	xx.x	xx.x	xx.x
Median	xx	xx	xx	xx
Q1, Q3	xx, xx	xx, xx	xx, xx	xx, xx
Min, Max	xx, xx	xx, xx	xx, xx	xx, xx

N = Number of subjects in a specific group; n = Number of subjects with data available; Percentages are based on N; SD: Standard deviation; Q1, Q3: First, third quartile; Min: minimum; Max: maximum.

Ventilator-free days are only counted through the date of early study discontinuation, study completion date or Day 28, whichever comes first. For subjects who die during the course of the study, number of ventilator-free days is defined as 0.

Page X of Y

(Notes for programmer:

Include only the categories of Days (0-28) in the table which are available in the data
)

Table 24: Time to last hospital discharge - ITT Set

	DSTAT 0.25 N=xxx	Cohort 1 PBO N=xxx	DSTAT 0.325 N=xxx	Cohort 2 PBO N=xxx
Number of subjects discharged from hospital, n (%) (a)	xx (xx.x)	xx (xx.x)	xx (xx.x)	xx (xx.x)
Kaplan-Meier estimates (b)				
Number of censored subjects, n (%) (b)	xx (xx.x)	xx (xx.x)	xx (xx.x)	xx (xx.x)
Number of subjects alive and still in hospital	xx (xx.x)	xx (xx.x)	xx (xx.x)	xx (xx.x)
Death	xx (xx.x)	xx (xx.x)	xx (xx.x)	xx (xx.x)
Time to hospital discharge (days) (b)				
25% Quartile (95% CI)	x.x (x.xx, x.xx)	x.x (x.xx, x.xx)	x.x (x.xx, x.xx)	x.x (x.xx, x.xx)
Median (95% CI)	x.x (x.xx, x.xx)	x.x (x.xx, x.xx)	x.x (x.xx, x.xx)	x.x (x.xx, x.xx)
75% Quartile (95% CI)	x.x (x.xx, x.xx)	x.x (x.xx, x.xx)	x.x (x.xx, x.xx)	x.x (x.xx, x.xx)

N = Number of subjects in a specific group; n = Number of subjects with data available; Percentages are based on N;
 (a) Subjects discharged from hospital will be counted as event.

(b) Kaplan-Meier estimates: Subjects discharged from hospital will be counted as event. Subjects who are still in the hospital or died in the hospital will be censored.

Time to hospital discharge (days): Days are calculated as (last hospital discharged date/time - first study drug date/time)/24h). Time will be censored at last individual date/time reported. If time is not available for events "23:59" will be imputed, for censored observations "00:01" will be imputed. Participants who died prior to hospital discharge will be censored at Day 28. Randomized untreated subjects will be censored with time to hospital discharge = 0.

(Notes for programmer: Subjects randomized not treated will be counted as censored observation (censor time = 0)
)

Page X of Y

Figure 8: Time to last hospital discharge (KM-Plot) - ITT Set

Kaplan-Meier Plot:

y-axis:

range: 0% to 100% by 20%
label: Event Probability
reference-line: 50%

x-axis:

range: 0 to xxx (depending on data), by 7 days
label: Time to Event (Days)

Lines:

solid
different colors/line styles for the treatment-groups
starting at (0%/Baseline)
Censored values marked

Footnote:

N = Number of subjects in a specific group; (+) = censored values;

Kaplan-Meier estimates: Subjects discharged from hospital will be counted as event. Subjects who are still in the hospital or died in the hospital will be censored.

Time to hospital discharge (days): Days are calculated as (last hospital discharged date/time - first study drug date/time)/24h).

Time will be censored at last individual date/time reported. If time is not available for events "23:59" will be imputed, for censored observations "00:01" will be imputed. Participants who died prior to hospital discharge will be censored at Day 28.

Randomized untreated subjects will be censored with time to hospital discharge = 0.

*(Notes for programmer: Subjects randomized not treated will be counted as censored observation (censor time = 0)
)*

Table 25: Time to first hospital discharge - ITT Set

For the layout refer to Table 24

Adapt footnote:

... Time to hospital discharge (days): Days are calculated as (first hospital discharged date/time - first study drug date/time)/24h)...

Figure 9: Time to first hospital discharge (KM-Plot) - ITT Set

For the layout refer to Figure 8

Adapt footnote:

... Time to hospital discharge (days): Days are calculated as (first hospital discharged date/time - first study drug date/time)/24h)...

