3. DERIVATIONS AND DEFINITIONS

Kaplan-Meier estimates

Time to xxx (days): Days are calculated as (start date/time – first study drug date/time)/24h). Time will be censored at last individual date/time reported.

Worst-case results in 2 scenarios for missing time-values:

1. Missing time for negative events will be imputed with “00:01”, missing time for censored observations will be imputed with “23:59”.

Negative events are:

- Time to first invasive mechanical ventilation or ECMO
- Time to first invasive mechanical ventilation, ECMO or all-cause mortality
- Time to all-cause mortality

2. Missing time for positive events will be imputed with “23:59”, missing time for censored observations will be imputed with “00:01”.

Positive events are:

- Time to clinical improvement
- Time to hospital discharge

In addition, to avoid bias in the positive events, deaths occurring prior to the positive event being observed will be censored at Day 28.

Ventilator-free days

Ventilator-free days are only counted from baseline through Day 28 or end of study, whichever comes first. They are derived based on the eCRF data collected on the Ventilator/Oxygen/Medical Care Status CRF page, Ventilator-free days are all days where Ventilator/Oxygen/Medical Care Status is not equal “Invasive Mechanical Ventilation or extracorporeal membrane oxygenation (ECMO)”.

Ventilator days are defined as cumulative rounded number of days with Ventilator/Oxygen/Medical Care Status = “Invasive Mechanical Ventilation or extracorporeal membrane oxygenation (ECMO)” divided by 24 h. Missing time for start will be imputed with “00:01”, missing time for stop will be imputed with “23:59”.

Study duration in days is defined as: Date of study completion (or date of early study discontinuation) – date of first study treatment + 1. For subjects randomized but not treated the date of randomization will be used instead of first study treatment date. The maximum study duration is set to 28 days, even if study completion or study discontinuation is after 28 days.

Ventilator-free days are defined as: study duration - number of ventilator days. For subjects who died during the course of the study, the number of ventilator-free days will be defined as 0.

Randomized, but not treated subjects:

The following rules will apply for randomized subjects without receiving study treatment, if not stated otherwise:

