- Calculations referring to start of treatment or baseline will be performed with respect to randomization date/time.
- Study duration in days is calculated as study discontinuation date - randomization date +1.
- In Kaplan-Meier analysis the “time-to” will be censored at 0.

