Table 18: Proportion of and time to invasive mechanical ventilation or all-cause mortality - ITT Set

	DSTAT 0.25 N=xxx	Cohort 1 PBO N=xxx	DSTAT 0.325 N=xxx	Cohort 2 PBO N=xxx
Number of subjects who are alive and free of invasive mechanical ventilation or ECMO through Day 28 (a)	xx (xx.x)	xx (xx.x)	xx (xx.x)	xx (xx.x)
Number of subjects with any invasive mechanical ventilation, ECMO, all-cause mortality or early study discontinuation, whatever comes first, n (%) (b)	xx (xx.x)	xx (xx.x)	xx (xx.x)	xx (xx.x)
Any invasive mechanical ventilation, ECMO	xx (xx.x)	xx (xx.x)	xx (xx.x)	xx (xx.x)
Death	xx (xx.x)	xx (xx.x)	xx (xx.x)	xx (xx.x)
Early study discontinuation < Day 25	xx (xx.x)	xx (xx.x)	xx (xx.x)	xx (xx.x)
Kaplan-Meier estimates (c)				
Number of censored subjects, n (%) (c)	xx (xx.x)	xx (xx.x)	xx (xx.x)	xx (xx.x)
Time to first invasive mechanical ventilation, ECMO or all-cause mortality (days) (c)				
25% Quartile (95% CI)	x.x (x.xx,x.xx)	x.x (x.xx,x.xx)	x.x (x.xx,x.xx)	x.x (x.xx,x.xx)
Median (95% CI)	x.x (x.xx,x.xx)	x.x (x.xx,x.xx)	x.x (x.xx,x.xx)	x.x (x.xx,x.xx)
75% Quartile (95% CI)	x.x (x.xx,x.xx)	x.x (x.xx,x.xx)	x.x (x.xx,x.xx)	x.x (x.xx,x.xx)

N = Number of subjects in a specific group; n = Number of subjects with data available; Percentages are based on N; ECMO: Extracorporeal membrane oxygenation.

(a) Early study discontinuation before Day 25 are not included.

(b) Subjects with any invasive mechanical ventilation, ECMO, all-cause mortality or early study discontinuation before Day 25 will be counted as event.

(c) Kaplan-Meier estimates: Subjects with any invasive mechanical ventilation, ECMO or all-cause mortality will be counted as event. All other subjects will be censored. Time to first invasive mechanical ventilation, ECMO or all-cause mortality, whatever comes first (days): Days are calculated as (start date/time - first study drug date/time)/24h). Time will be censored at last individual date/time reported. If time is not available for events "00:01" will be imputed, for censored observations "23:59" will be imputed. Randomized untreated subjects will be censored at time = 0.

Page X of Y

(Notes for programmer: Subjects randomized not treated will be counted in

- a) as failure, and therefore not included in (a)
- b) as event (in the line "Early study discontinuation < Day 25") in case of early study discontinuation < Day 25
- c) as censored observation (censor time = 0)

)

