(b) Kaplan-Meier estimates: Subjects who died will be counted as events. All other subjects will be censored. Time to all-cause mortality (days): Days are calculated as (start date/time - first study drug date/time)/24h). Time will be censored at last individual date/time reported. If time is not available for events "00:01" will be imputed, for censored observations "23:59" will be imputed. Randomized untreated subjects will be censored at time = 0.

Page X of Y

(Notes for programmer: Subjects randomized not treated will be counted in

- a) as event (in the line "Early study discontinuation < Day 25") in case of early study discontinuation < Day 25
- b) as censored observation (censor time = 0)

)

Figure 6: Time to all-cause mortality (KM-Plot) - ITT Set

Kaplan-Meier Plot:

y-axis:

range: 0% to 100% by 20%
label: Event-free Probability
reference-line: 50%

x-axis:

range: 0 to xxx (depending on data), by 7 days
label: Time to Event (Days)

Lines:

solid
different colors/line styles for the treatment-groups
starting at (100%/Baseline)
Censored values marked

Footnote:

N = Number of subjects in a specific group; (+) = censored values;

Kaplan-Meier estimates: Subjects who died will be counted as event. All other subjects will be censored.

Time to all-cause mortality (days): Days are calculated as (start date/time - first study drug date/time)/24h). Time will be censored at last individual date/time reported. If time is not available for events "00:01" will be imputed, for censored observations "23:59" will be imputed. Randomized untreated subjects will be censored at time = 0.

*(Notes for programmer: Subjects randomized not treated will be counted as censored observation (censor time = 0)
)*

Table 20: Proportion of participants who are alive, discharged from the hospital, and not using home oxygen - ITT Set

Visit	DSTAT 0.25 N=xxx n (%)	Cohort 1 PBO N=xxx n (%)	DSTAT 0.325 N=xxx n (%)	Cohort 2 PBO N=xxx n (%)
Day 8 (D8)	xx (xx.x)	xx (xx.x)	xx (xx.x)	xx (xx.x)
Day 14 (D14)	xx (xx.x)	xx (xx.x)	xx (xx.x)	xx (xx.x)
Day 28 (D28)	xx (xx.x)	xx (xx.x)	xx (xx.x)	xx (xx.x)

N = Number of subjects in a specific group; n = Number of subjects with data available;

Subjects who discontinued study early prior to start of time window (-3 days to -1 day for each visit) will be considered as failures even if alive and last records indicate no oxygen and out of hospital.

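### The ITT-labelled Kaplan-Meier outputs discard all follow-up of randomised but untreated participants, and Table 18 rows (a) and (b) disagree for one such case

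*SAP*

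**What the plan says.** SAP section 3 has a short list of rules for randomised participants who never received study drug, applying unless another rule is stated. One sets the time origin: "Calculations referring to start of treatment or baseline will be performed with respect to randomization date/time". Another covers survival curves: "In Kaplan-Meier analysis the “time-to” will be censored at 0".

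Section 5.2 repeats the second rule in Tables 18, 19 and 22 and Figures 5 to 7 ("Randomized untreated subjects will be censored at time = 0"), and in equivalent words in Table 24 and Figure 8. Table 25 and Figure 9 inherit it by reference. All are titled as ITT-set outputs, and Protocol 9.3 defines ITT as everyone randomised, in the assigned group. The same footnotes also carry a general event rule; for mortality in Table 19 it is "Subjects who died will be counted as events".

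Table 18 has two complementary count rows. Row (a) counts participants alive and free of invasive ventilation or ECMO, with the footnote "Early study discontinuation before Day 25 are not included". Row (b) counts those with ventilation, ECMO, death or study discontinuation before Day 25. The programmer notes then treat untreated participants differently in the two rows. For row (a) they count "as failure, and therefore not included in (a"), without condition. For row (b) they count as an event "in case of early study discontinuation < Day 25".

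**The concern.** An ITT output should use what was observed after randomisation, treated or not. Protocol 7.3 expects every randomised participant to be followed through Day 28 whether or not study drug was completed, so follow-up on an untreated person is the expected case. The time-0 rule discards it, including deaths and intubations, although section 3 already supplies a randomisation origin that would allow it to be used.

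Other ITT outputs in the same section treat this person conditionally. Tables 20 and 21 assign failure or missing only on discontinuation before the visit window. For ventilator-free days (Table 23), "For subjects randomized but not treated the date of randomization will be used instead of first study treatment date". So an untreated participant discharged without oxygen and followed to Day 28 is a success in Table 20 and is censored at time 0 in Tables 24 and 25.

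At stake is whether the ITT curves and quartiles describe the ITT set, and whether Table 18 adds up. The sponsor may unblind and review these cohorts, and with arms of 4 to 8 one participant moves a curve visibly.

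**Working it through.** The plan states no figure on this point, so there is none to reproduce. The check applies the SAP rules to assumed cases.

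**Inputs.** Arm sizes: Cohort 1 is 6/6. Cohort 2 is 8/4 in Protocol 4.1 and 6/6 in SAP section 2, so n = 8, 6 and 4 are shown. The number of untreated participants is not given; one per arm is assumed. Everyone else is censored at Day 28 unless stated.

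**Step 1: what censoring at 0 does.** The estimate is S(28) = Π(1 − d_j/n_j) over event times t_j > 0, with d_j events among n_j at risk. A person censored at 0 is in no risk set, so the estimate equals that from the n − 1 treated participants. The displayed N and the censored count still include the person.

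**Step 2: Day 28 event-free estimate.** *Observed* times the untreated person from randomisation and counts the event; *SAP rule* censors at 0.

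| Case | n | Observed | SAP rule | Difference (points) |
|---|---|---|---|---|
| A. Untreated person has the only event | 8 | 7/8 = 87.5% | 100% | +12.5 |
| | 6 | 5/6 = 83.3% | 100% | +16.7 |
| | 4 | 3/4 = 75% | 100% | +25 |
| B. Untreated event at 0.5 d, one treated event at 5 d | 8 | 6/8 = 75% | 6/7 = 85.7% | +10.7 |
| | 6 | 4/6 = 66.7% | 4/5 = 80.0% | +13.3 |
| | 4 | 2/4 = 50% | 2/3 = 66.7% | +16.7 |
| C. Untreated event-free to Day 28, one treated event at 5 d | 8 | 7/8 = 87.5% | 6/7 = 85.7% | −1.8 |
| | 6 | 5/6 = 83.3% | 4/5 = 80.0% | −3.3 |
| | 4 | 3/4 = 75% | 2/3 = 66.7% | −8.3 |
| D. Untreated leaves at once, one treated event | 8, 6, 4 | 85.7%, 80.0%, 66.7% | same | 0 |

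The direction depends on the untreated person's outcome.

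**Step 3: tabulated quartiles.** In case B with n = 6 the 25% quartile is 5 days observed and not reached under the rule. In cases A and C with n = 8 or 6, every estimate stays above 75%, so the quartile is not reached either way.

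**Step 4: positive events (Tables 22, 24, 25).** Section 3 censors deaths before improvement or discharge at Day 28, to avoid bias. An untreated death meets both that rule and the time-0 rule. If all n − 1 treated participants succeed, Day 28 censoring gives a cumulative probability of (n − 1)/n = 87.5%, 83.3% or 75%. Time-0 censoring gives 100%.

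**Step 5: Table 18 rows for an untreated participant.**

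| Untreated participant | In row (a)? | In row (b)? | Rows agree? |
|---|---|---|---|
| Event-free, discontinued before Day 25 | No | Yes | Yes |
| Ventilation, ECMO or death observed | No | Yes (footnote b) | Yes |
| Event-free, followed to Day 25 or later | No | No | No: (a) + (b) = N − 1 |

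In the third case, with no other failures, row (a) shows 7/8 = 87.5%, 5/6 = 83.3% or 3/4 = 75% instead of 100%, while row (b) is 0. Row (a) is understated by 12.5, 16.7 or 25 points.

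**Step 6: Table 24 counts.** The censored sub-lines are for participants alive and still in hospital and for deaths. An untreated participant who was discharged fits neither. If row (a) counts that person, as its footnote says, and everyone is discharged, then row (a) plus censored is 8 + 1 = 9 of 8, 7 of 6 or 5 of 4. Table 22 has the same difficulty for an untreated participant who improved.

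**The case against.** The strongest reply is that the rule is deliberate and disclosed. SAP version 2.0 was issued partly to clarify the handling of untreated participants, and the footnotes state the rule. Within section 3 the Kaplan-Meier line can be read as a specific exception to the general origin rule. That answers a charge of accidental contradiction. It does not make it sound to discard observed events in an ITT output when an origin is available.

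Several points limit the size, and they stand:

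- The tables report counts and quartiles. A Day 28 percentage could only be read from the plotted curves, and Step 3 shows that the quartiles often do not move.
- The larger differences mostly reflect what one person weighs in an arm of 4 to 8.
- The number of untreated participants is unknown. The programmer notes suggest the authors had early leavers in mind, for whom the curves do not change.
- The excess count in Step 6 depends on the reading. The programmer notes for Tables 22 and 24 are not tied to a row, and could be taken to remove the person from row (a). The counts then add up, but an observed discharge or improvement is lost and no censored sub-line fits.

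For Table 18 it can be argued that counting untreated participants as failures is a conservative convention and that the SAP never requires the rows to sum to N. But the rows are complementary by definition, and Protocol 9.4.1 imputes failure for missing data, not for an observed success.

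Removing the rule also mixes two time origins in one curve. That is a real but small cost.

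**Conclusion.** The point holds on both counts, at minor severity. The time-0 rule turns the ITT-labelled Kaplan-Meier outputs (Tables 18, 19, 22, 24 and 25, Figures 5 to 9) into treated-only estimates whenever an untreated participant has follow-up. Table 18 rows (a) and (b) disagree in the single case of an untreated, event-free participant followed to Day 25 or later.

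The sizes in Steps 2 and 5 rest on one assumed untreated participant per arm. The reading of the SAP text is certain; whether the problem arises in the data is not.

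Protocol 9.4 makes the Cohort 1 and 2 analysis descriptive. Alpha, power and Phase 3 inference are not affected, and neither are Table 7 and Figures 1 and 2, which use the Safety Set. Untreated participants' observed outcomes still appear in Tables 6, 18(b), 19(a), 20, 21 and 23. Protocol 9.4.2 censors losses at last follow-up, which points the same way, but it is written for Phase 3 with similar methods for Phase 2, and the conclusion does not rely on it.

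**What to change.** 1. Delete the time-0 censoring rule from SAP section 3 and from the footnotes and programmer notes in section 5.2. For untreated participants, use randomisation date/time as the Kaplan-Meier origin, count observed events, and otherwise censor at last contact. Keep the existing Day 28 censoring of deaths that precede a positive event.
2. In Table 18 row (a), make an untreated participant a failure only on observed ventilation or ECMO, death, or study discontinuation before Day 25, as in row (b).
3. Add a footnote that time runs from first dose for treated and from randomisation for untreated participants.

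If the sponsor prefers to keep the rule, the Kaplan-Meier titles should say that follow-up of untreated participants is excluded. The Table 18 change is needed either way.

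The cost is a few words of SAP text and a few lines of programming. The dates are already collected, and Tables 20 and 21 have conditional wording to adapt. Randomisation and bolus are both scheduled for Day 1, so the difference between the two origins should be short.

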Abbreviations: aPTT=activated partial thromboplastin time; D=day; INR=international normalized ratio; NIAID (ordinal scale)= National Institute of Allergy and Infectious Diseases (scale used in Study NCT04280705); PT=prothrombin time; HMGB1=high mobility group box protein 1; IL-6=interleukin-6; SAA=serum amyloid A; TNF $\alpha$ =tumor necrosis factor alpha

a Recommend following guidelines of American College of Cardiology. Day 3 ECG not required if participant is on continuous telemetry. Perform unscheduled ECG if irregular heart rhythm on exam or telemetry.

b Refer to Section 8.3.4 and Table 4 for complete list of laboratory tests. Chemistry includes alanine aminotransferase, aspartate aminotransferase, alkaline phosphatase, bilirubin (total and direct), blood urea nitrogen, C-reactive protein, creatinine (with calculated creatinine clearance or estimated glomerular filtration rate), calcium, ferritin, lactate dehydrogenase, magnesium, potassium, and sodium. Hematology includes platelet count, hemoglobin, absolute neutrophil count, and white blood cell count with differential. In the event of thrombocytopenia, refer to the evaluation algorithm in Appendix 6 for additional laboratory tests to diagnose/rule out heparin-induced thrombocytopenia.

c Do not draw blood for aPTT or PK analyses from the same line that is used for study intervention administration. Drawing blood from a heparinized line may falsely alter results obtained; therefore, if using an indwelling catheter, draw approximately 5 mL of blood from the line for discard before drawing the aPTT and PK samples.

d Draw blood for aPTT measurements no sooner than 8 hours after the bolus dose. During the continuous infusion, aPTT should be measured a minimum of once daily; more frequent monitoring is recommended when feasible based on the clinical status of the participant.

e Record date AND time for each change in individual components of the assessment: mechanical ventilation start/stop, high flow/mask oxygen start/stop, nasal oxygen start/stop, hospital discharge (whether with limitations, or without limitations), and death.

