### 5.1. Inclusion Criteria

A potential participant must meet **all** the following criteria to be included in the study:

1. Hospitalized for laboratory-documented COVID-19 disease (e.g., positive for SARS-CoV-2 via nasopharyngeal swab RT-PCR [or other commercial or public health assay]).
2. Age  $\geq$ 18 years and  $\leq$ 85 years.
3. Resting oxygen saturation (SaO2) of <94% while breathing ambient air.
4. Score of 3 or 4 on the NIAID ordinal scale (requires supplemental oxygen or noninvasive ventilation) (see [Appendix 4](#)).
5. Provide informed consent to participate in the study (by participant or legally-acceptable representative).

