## 11.4. Appendix 4: NIAID Ordinal Scale

The ordinal scale is an assessment of the clinical status of the participant at a given time point. The scale is as follows:

1. Death
2. Hospitalized, on invasive mechanical ventilation or extracorporeal membrane oxygenation (ECMO)
3. Hospitalized, on noninvasive ventilation or high flow oxygen devices
4. Hospitalized, requiring supplemental oxygen
5. Hospitalized, not requiring supplemental oxygen; requiring ongoing medical care (COVID-19 related or otherwise)
6. Hospitalized, not requiring supplemental oxygen; no longer requires ongoing medical care
7. Not hospitalized, limitation on activities and/or requiring home oxygen
8. Not hospitalized, no limitations on activities

Note: This scale is being used for the primary endpoint in the Adaptive COVID-19 Treatment Trial (ACTT; NCT04280705), sponsored by the National Institute of Allergy and Infectious Diseases (NIAID).

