- Determine status on particular day with respect to death, hospitalization, and ventilatory care status. For example, if a subject starts nasal supplemental oxygen on Day -1 and stops on Day 10, and if the subject is still in hospital at Day 8, a NIAID score = 4 to be assigned at Day 8.
- If can't determine one, pick the worst status on that day.
For example nasal supplemental oxygen stops on Day 8, and subject does not require oxygen but requires ongoing medical care starting on Day 8, and the subject is in hospital at Visit Day 8, a NIAID score = 4 to be assigned at Day 8.
- For subjects who discontinued study early within the time window (-3 days to -1 day for each visit), the last available NIAID score will be used at the corresponding visit and a NIAID score = missing will be assigned to all visits after early study discontinuation date.
E.g. if a subject withdraws from study on Day 7, his or her last NIAID score will be assigned to Day 8, and NIAID scores at Day 14 and Day 28 are considered as missing. If subject withdrawal on Day 8, his or her Day 8 NIAID score will be assigned to Day 8, and NIAID scores at Day 14 and Day 28 are considered as missing.
- For subjects who died e.g. prior to or on Day 8 a NIAID score = 1 will be assigned for the visits on and after Day 8
- Subjects randomized not treated will be counted as missing at the respective visit in case of early study discontinuation prior to start of the time window (-3 days to -1 day for each visit).
)

Table 22: Time to clinical improvement - ITT Set

	DSTAT 0.25 N=xxx	Cohort 1 PBO N=xxx	DSTAT 0.325 N=xxx	Cohort 2 PBO N=xxx
Number of participants with clinical improvement, n (%) (a)	xx (xx.x)	xx (xx.x)	xx (xx.x)	xx (xx.x)
Kaplan-Meier estimates (b)				
Number of censored subjects, n (%) (b)	xx (xx.x)	xx (xx.x)	xx (xx.x)	xx (xx.x)
Number of subjects without improvement	xx (xx.x)	xx (xx.x)	xx (xx.x)	xx (xx.x)
Death	xx (xx.x)	xx (xx.x)	xx (xx.x)	xx (xx.x)
Time to clinical improvement (days) (b)				
25% Quartile (95% CI)	x.x (x.xx,x.xx)	x.x (x.xx,x.xx)	x.x (x.xx,x.xx)	x.x (x.xx,x.xx)
Median (95% CI)	x.x (x.xx,x.xx)	x.x (x.xx,x.xx)	x.x (x.xx,x.xx)	x.x (x.xx,x.xx)
75% Quartile (95% CI)	x.x (x.xx,x.xx)	x.x (x.xx,x.xx)	x.x (x.xx,x.xx)	x.x (x.xx,x.xx)

N = Number of subjects in a specific group; n = Number of subjects with data available; Percentages are based on N; Clinical improvement is defined as at least a 2-grade improvement from baseline on the NIAID ordinal score.

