(a) Subjects with a clinical improvement will be counted as event.

(b) Kaplan-Meier estimates: Subjects with a clinical improvement will be counted as event. Subjects without a clinical improvement or deaths occurring prior to the positive event will be censored. Time to clinical improvement: Days are calculated as (start date/time - first study drug date/time)/24h. Time will be censored at last individual date/time reported. If time is not available for events "23:59" will be imputed, for censored observations "00:01" will be imputed. Participants who died prior to Day 28 without clinical improvement will be censored at Day 28. Randomized untreated subjects will be censored at time = 0.

Page X of Y

(Notes for programmer: Subjects randomized not treated will be counted as censored observation (censor time = 0)
)

Figure 7: Time to clinical improvement (KM-Plot) - ITT Set

Kaplan-Meier Plot:

y-axis:

range: 0% to 100% by 20%
label: Event Probability
reference-line: 50%

x-axis:

range: 0 to xxx (depending on data), by 7 days
label: Time to Event (Days)

Lines:

solid
different colors/line styles for the treatment-groups
starting at (0%/Baseline)
Censored values marked

Footnote:

N = Number of subjects in a specific group; (+) = censored values;

Clinical improvement is defined as at least a 2-grade improvement from baseline on the NIAID ordinal score.

Kaplan-Meier estimates: Subjects with a clinical improvement will be counted as event. Subjects without a clinical improvement or deaths occurring prior to the positive event will be censored.

Time to clinical improvement (days): Days are calculated as (start date/time - first study drug date/time)/24h). Time will be censored at last individual date/time reported. If time is not available for events "23:59" will be imputed, for censored observations "00:01" will be imputed. Participants who died prior to Day 28 without clinical improvement will be censored at Day 28. Randomized untreated subjects will be censored at time = 0.

(Notes for programmer: Subjects randomized not treated will be counted as censored observation (censor time = 0)

)

Table 23: Number of ventilator-free days from baseline through Day 28 - ITT Set

	DSTAT 0.25 N=xxx	Cohort 1 PBO N=xxx	DSTAT 0.325 N=xxx	Cohort 2 PBO N=xxx
Number of ventilator-free days, n(%)				
0	xx (xx.x)	xx (xx.x)	xx (xx.x)	xx (xx.x)
1	xx (xx.x)	xx (xx.x)	xx (xx.x)	xx (xx.x)
2	xx (xx.x)	xx (xx.x)	xx (xx.x)	xx (xx.x)
3	xx (xx.x)	xx (xx.x)	xx (xx.x)	xx (xx.x)

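### SAP Tables 22, 24 and 25 score a participant discharged for end-of-life care who dies by Day 28 as an early improvement and discharge, because the death rule covers only deaths before the event

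*SAP*

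**What the plan says.** SAP Section 3 gives the rule for deaths in the positive-event analyses and its purpose: "to avoid bias in the positive events, deaths occurring prior to the positive event being observed will be censored at Day 28".

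The Table 22 footnotes (SAP Section 5.2) apply it to time to clinical improvement. The event is set by "Clinical improvement is defined as at least a 2-grade improvement from baseline on the NIAID ordinal score". Censoring is set by "Subjects without a clinical improvement or deaths occurring prior to the positive event will be censored", and the deaths moved to the end of follow-up are limited: "Participants who died prior to Day 28 without clinical improvement will be censored at Day 28". No sustained improvement and no survival after the event is required.

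For time to hospital discharge, the Table 24 footnote reads "Subjects discharged from hospital will be counted as event". It sets no condition on destination. Censoring is for participants still in hospital or who died there, and only deaths before discharge are placed at Day 28. Table 25 copies this layout for first discharge.

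The SAP derives NIAID scores from Protocol Appendix 4, where grade 7 is "Not hospitalized, limitation on activities and/or requiring home oxygen". Protocol Table 1, footnote e, asks sites to record the date and time of "hospital discharge (whether with limitations, or without limitations), and death". It names no discharge destination. Neither document mentions hospice, palliative or end-of-life discharge.

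**The concern.** The SAP says that its death rule exists to prevent bias. Without it, a death censored when it occurs would drop out of the risk set as if the participant might still have improved. Holding deaths to Day 28 treats them as never improving. That works only if every death by Day 28 reaches the rule.

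A participant who leaves hospital to die does not reach it. The discharge comes first and closes the record as a success, and the later death changes nothing in these three tables. Two participants with the same fatal course get opposite results depending on where they die. The extra favourable events fall among the sickest participants, so they flatter whichever arm has more terminal discharges.

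Protocol Section 9.4.2 leaves the handling of deaths, endpoint by endpoint, to the SAP. Death after discharge is not addressed for Tables 22, 24 and 25.

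**Working it through.** The plan states no figure on this point, so there is none to reproduce. The check applies its rules as written.

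**1. Does discharge meet the improvement definition?** Entry requires a score of 3 or 4 (Protocol Section 5.1). A living participant out of hospital scores at least 7 (Appendix 4). The gain is 7 − 3 = 4 or 7 − 4 = 3 grades. Both meet the 2-grade threshold.

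**2. One assumed record through the tables.** Discharged for end-of-life care on study Day 10, not readmitted, dies on Day 14:

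| SAP output | Result |
|---|---|
| Table 22, clinical improvement | Event, dated at the discharge |
| Tables 24 and 25, last and first discharge | Event, dated at the discharge |
| Table 18, ventilation or death | Failure |
| Table 19, mortality | Death |
| Table 21, NIAID score | 1 at Days 14 and 28 |
| Table 23, ventilator-free days | 0 |

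The Day 28 death rule is not triggered, because the death follows the event. The fixed-day tables are not always on the unfavourable side. With discharge on Day 6 and death on Day 9, Table 21 shows grade 7 at Day 8, and Table 20 shows a Day 8 success if the participant is off oxygen.

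**3. Size in the arms this SAP covers.** Protocol Section 4.1 gives 6 and 6 in Cohort 1, and 8 and 4 in Cohort 2. One participant moves an arm's proportion by 100/n points:
- n = 4: 100/4 = 25.0
- n = 6: 100/6 = 16.7
- n = 8: 100/8 = 12.5

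SAP Section 2 still lists 6 and 6 for Cohort 2; that would give 16.7, inside the same range.

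**4. Effect on the Kaplan-Meier curve, assumed data.** Times are days from first dose. Each arm has one terminal discharge at day 10, and all other non-improvers are censored at day 28.
- n = 6, genuine improvements at days 7 and 9. As written, survival is 5/6 × 4/5 × 3/4 = 0.50, so the curve reaches 50% at day 10. With the terminal discharge held to day 28, it is 5/6 × 4/5 = 0.667, so the curve stops at 33.3%.
- n = 8, genuine improvements at days 6, 8 and 9. As written, 4/8 = 50.0%; after the change, 3/8 = 37.5%.
- n = 4, one genuine improvement at day 7. As written, 2/4 = 50.0%; after the change, 1/4 = 25.0%.

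In each case, the curve reaches 50% as written and never reaches it after the change.

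**The case against.** The strongest reply is that the plan does what it says. An endpoint called time to hospital discharge counts discharges, the NIAID scale is taken over from another trial, and the death rule is expressly limited to deaths before the event. Every such death is still held to Day 28. This stands: a reader might infer that the SAP's death rule is defeated, and the documents do not support that. What remains is that the SAP gives bias avoidance as the rule's purpose, and this subgroup falls outside it.

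Second, one participant moves any arm of 4 to 8 by 12.5 to 25 points, so that size is not special to this problem. True. It shows only that a single case is visible in these tables.

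Third, much is visible elsewhere. Table 2 lists each death and its date, deaths count in Tables 18 and 19, and a readmission followed by an in-hospital death has a route to censoring in Table 24. The full eCRF was not supplied, so footnote e does not prove that destination goes unrecorded. An inpatient hospice unit might also be read as still hospitalized. These points mean that cases can probably be found; they do not change how Tables 22, 24 and 25 score them.

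Fourth, Protocol exclusion 12 removes people whose 6-month mortality from malignancy or another irreversible condition is estimated at 50% or more. It lowers the number of such discharges, but it acts at entry and does not cover later deterioration from COVID-19.

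**Conclusion.** The gap is real and minor. Read literally, Tables 22, 24 and 25 score a terminal discharge followed by death by Day 28 as an early favourable outcome, while Tables 18, 19 and 23 score the same participant as a failure, a death and 0 ventilator-free days. Table 21 gives score 1 at visits on or after the death. The primary endpoint and all-cause mortality through Day 28 are not affected.

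The size depends on how often this happens, which the documents do not say. The Kaplan-Meier examples are illustrations on assumed data.

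A reader might also infer that the error could reverse a real benefit in the Phase 3 log-rank and Cox analyses, or scale it to the 450 Phase 3 participants. The documents support neither. This SAP governs only the post-Cohort 1/2 lock analysis, Protocol Section 9.4 makes that analysis descriptive, these shells hold no p-value or hazard ratio, and the Phase 3 SAP is a separate document that was not supplied. The Phase 3 concern arises only if that SAP copies these rules.

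**What to change.** In SAP Section 3 and the footnotes of Tables 22, 24 and 25, state that discharge to hospice or for end-of-life care is not a positive event and is censored at Day 28 like other deaths. For these tables, this also settles how a transfer to an inpatient hospice unit is treated.

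For data already collected, identify the cases as discharge followed by death by Day 28 without readmission. Confirm each from the death report, since Protocol Section 8.4.5 already requires date, cause and supporting information. The confirmation keeps unexpected deaths at home from being reclassified. This search misses hospice participants still alive at Day 28, and the SAP should say so.

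Carry the rule into the Phase 3 SAP. If the eCRF does not already record discharge destination, add it.

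The cost is one SAP sentence with matching footnotes, at most one extra field for sites, and a small manual review.
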